5.6.4 Loss to Follow-up

Every effort will be made by the research teams at sites to establish rapport with participants and/or consultees to emphasise the importance of trial procedures and follow up. Where patients may be discharged to a known community hospital setting, every attempt will be made to continue the trial with the participant and assessors will travel to patients' for follow up appointments at T1 and T2 if necessary.

5.6.5 Trial Closure

The end of the trial is defined as 6 months following the last follow-up visit of the last participant randomised, to allow for data entry and data cleaning activities to be completed.

5.7 Sample Size

The efficacy study is powered to detect a significant change from baseline to T1 between the intervention and control groups for the primary outcome of the Star Cancellation sub-test of the BIT [43]. Our sample size calculation is directly informed by our published proof-ofconcept study [16] which found that the SIGHT+TAU group (N=10) had significantly greater neglect improvement on the BIT than the SHAM+TAU group (N=10; $F_{(1,18)}$ =6.7, p=0.018, partial n²_p=0.27; see Fig.1). Specifically, informed by this data we have assumed an effect of size of 0.6 (equivalent to partial n²_p=0.27 [16]). Stroke (and neglect) recovery takes place most rapidly over the first 7 days post-stroke and has been shown to decrease at around 3 months post-stroke [32]. Early after stroke, it has been reported that between 2-days and 9days post-stroke, 33% of patients with neglect significantly improve in the Star Cancellation Test (median Star Cancellation score at 2 days=31 and 9 days=47; cut-off=51; max=54), with 67% showing poor recovery (median Star Cancellation score at 2 days=26 and 9 days=35). The c-SIGHT feasibility trial data [17] shows that at 3-months post-stroke, 42% of neglect patients have recovered on the Star Cancellation Test (median score at 3 months=53) in line with a recent meta-analysis of 12 studies (N=262 patients, [85]). Thus, to accommodate the additional 10-15% natural recovery rate between 1-week and 3-months post-stroke, we reduced our effect size from 0.6 (estimated from PoC data at 3 months poststroke [16]) by 15% to 0.51, which with 90% power at the 5% level of significance using a two-sample t-test requires 206 participants (103 per group), including a 20% dropout. The effect size of 0.51 represents a difference of approximately 6.1 points on the Star Cancellation sub-test assuming a SD of approximately 12 obtained from our previous studies [16,17]. As the proposed trial compares SIGHT+TAU and TAU alone we expect our effect size to be larger than the one found in our proof-of-concept study [16]. Natural recovery is further accounted for in the design as some neglect improvement will occur in both experimental and control groups in a similar way since they are balanced for neglect severity - a strong predictor of stroke recovery [38; see randomisation strata]. The intervention effect is additional to natural recovery. The 20% dropout rate is based on our feasibility trials in post-stroke neglect with an average of 17.5% dropout in experimental arm at the 12-week post-intervention follow-up (15% [17] and 20% [56]).

Regarding the mechanistic brain imaging, a sample of 40 per group, which includes 20% attrition, will provide greater than 90% power at 2.5% level of significance (as we have 2 correlations the significance level is adjusted) to detect a correlation of 0.58 between IPS structure and function and treatment response in each arm separately. This sample size is directly informed by published data showing that interhemispheric (left-right) functional

connectivity between the IPS and the rest of the brain predicts neglect improvement at 12weeks post-stroke (r=0.58; p<0.001, N=25 neglect patients [28]). Importantly, the total sample size of 80 for the brain imaging study is feasible within our timeframe based on the FAST-Indicate EME stroke trial [55] and the published rates of 45% for MRI attrition in acute stroke [61]. Specifically, we expect that approximately 112 of the 206 recruited participants will be able and consent to undergo MRI and thus our sample size of 80 is achievable.

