4.2 Objectives

This multicentre RCT aims to investigate the clinical efficacy of SIGHT on post-stroke neglect when delivered by a therapist in tightly controlled within-hospital settings, whilst simultaneously determining the causes of differing responses to therapy between individuals. Our primary research aims are to:

(1) determine whether SIGHT in addition to TAU produces greater reduction in neglect than TAU alone (i.e., standard occupational therapy for neglect).

(2) determine whether benefits from SIGHT are still evident at the 12-week follow-up after the intervention ends.

(3) determine if therapy response is modified by: (a) lesion location; (b) left and right IPS functional connectivity; (c) left and right IPS structural connectivity; (d) perception-grasping dissociation; (e) stroke severity, (f) visual and/or (g) cognitive deficits.

Our testable hypotheses, generated by our early phase work and neuroimaging studies [16,19-20,26-27], are that:

(1) when added to treatment as usual (TAU), 30 minutes/day of SIGHT for 7 days (over a 10-day period) will produce greater reduction in neglect than TAU alone.

(2) patients with impaired IPS structure or function will benefit less from SIGHT.

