- The OCS is an established quick (15min) cognitive screen consisting of 10 tasks encompassing five cognitive domains: attention and executive function, language, memory, number processing, and praxis [45]. The OCS was devised to be inclusive and un-confounded by aphasia and neglect. The OCS offers advantages over other screening tools in terms of ease of completion and feasibility for stroke survivors with physical, language or visuospatial impairments [69]. Moreover, the OCS is more sensitive than the Mini Mental State Examination at detecting cognitive deficits poststroke [70] and assesses stroke-specific cognitive deficits not assessed by the Montreal Cognitive Assessment or the Addenbrookes Cognitive Examination [71].
- The gesture recognition sub-test of the BCoS (5min) will be used to provide quick and valid way to detect apraxia using procedures designed to be inclusive for patients with aphasia and/or spatial neglect [76]. Participants will view familiar gestures (object and non-object related) and asked to choose their meaning. As we are recruiting both right, left and bilateral hemisphere strokes this will help examine whether those with apraxia in our sample are able to benefit from SIGHT.
- **CENT** (5min) is a sensitive computerised 'aphasia friendly' measure of neglect of far space (or extrapersonal neglect) that has been validated in stroke and shown to predict stroke recovery and ADL deficits [77,87]. Participants are asked to use a mouse to click on targets on a screen. The scores are automatically generated.
- The clinical brain imaging scans (CT and/or MRI) and their reports will be extracted and used to map the stroke lesion location. Lesions will be manually delineated by UEA team on the structural scan using open-source cross-platform medical image viewers such as MRICROn 72]. Then, the checked lesion maps will be normalized to stereotaxic space using the age-specific template within the Statistical Parametric Mapping Software (SPM) clinical toolbox developed for stroke lesion-symptom mapping studies [73]. Routine clinical brain scans have been demonstrated to be of sufficient quality for lesion mapping research [74-75] and will ensure that lesion mapping can be performed for the full sample (N=206), instead of only those who complete the MRI (N=80), giving us sufficient power (minimum recommended N=100 [75]) for determining the lesion locations significantly associated with lower therapy response.

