Anonymised neuroimaging data will be sent to UEA research team via the Image Exchange Portal and processed using specialist software such as SPM and FSL. We will use well-established pre-processing routines for motion-correction, coregistration, smoothing and temporal filtering, and standardised pipelines that facilitate comparisons across studies (e.g., fMRIprep). Regions of interest (ROIs) will be manually identified in each participant in left and right IPS (seed regions) by visual inspection of the T1 using established anatomical landmarks and then centring a sphere closest to the peak coordinates associated with neglect improvement [28]. ROIs overlapping with lesion will be excluded from analysis.

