The evaluation of mechanistic determinants of response to therapy will be modelled using a general linear model using the following baseline data: structural connectivity as per fractional anisotropy of fibres connecting IPS seed-regions and defined areas in the rest of the brain; inter-hemispheric (left-right) functional connectivity as per time course correlations between IPS seed-regions and rest of the brain; perception-grasping score computed from difference in deviation from rod centre between grasping and perception; stroke severity; visual field VISA sub-test score; and, OCS domain scores. To determine if treatment effect is modified by these mechanistic variables, we will correlate change scores (from baseline to T1, i.e. therapy response; Fig.2) and each of these measures while regressing out lesion volume (computed from the lesion map) as lesion size correlates with stroke recovery [28]. Each data will be included separately and then data reduction methods will be applied so that all the measures can be included in a single model. The study investigating IPS will test effects in each arm separately as well as test for an interaction to see if the association is different in the two arms. In addition, to determine if lesion location predicts treatment response (hypothesis 2), we will use lesion-symptom mapping analysis and test if specific lesion sites are associated with smaller change scores/therapy response.

If patients receive less than 70% of the intervention, they will be included in the intention-totreat efficacy analysis and T1 and T2 measures will still be collected and included in the mechanistic analysis to predict overall neglect recovery. An additional per-protocol analysis will be conducted in which these individuals will be excluded so that we can differentiate the effect of being allocated to the intervention (the intention-to-treat analysis) and the effect of the intervention if the participant, and therapist, adhere (the per-protocol analysis).

Site will be used as strata for the randomisation; this should remove any potential confounding for TAU variation across sites. In the analysis we will report the 'dose' given to the participants. We will carry out a per-protocol analysis including individuals who have received an appropriate dose of SIGHT (>70%). In the intervention group, we will correlate the amount of therapy received against the change in the primary outcome measure.

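### The imaging power in 5.7 covers one within-arm correlation, not whether IPS measures or lesion site modify the effect of SIGHT

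*Protocol*

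**What the plan says.** Protocol 5.7 sets the imaging sub-study at "a sample of 40 per group, which includes 20% attrition". It claims "greater than 90% power at 2.5% level of significance (as we have 2 correlations the significance level is adjusted"), and the target is "to detect a correlation of 0.58 between IPS structure and function and treatment response in each arm separately". The effect size comes from a published cohort in which IPS functional connectivity "predicts neglect improvement at 12weeks post-stroke (r=0.58; p<0.001, N=25 neglect patients [28"]).

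Protocol 4.2 frames the question differently. Objective 3 asks whether response to therapy is modified by several factors, among them "b) left and right IPS functional connectivity; (c) left and right IPS structural connectivity". Hypothesis 2 is that patients with impaired IPS structure or function gain less from SIGHT.

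Protocol 5.10.4.1 treats the change from baseline to T1 as therapy response. To judge modification it correlates that change with each baseline measure, regressing out lesion volume. For IPS it will "test effects in each arm separately as well as test for an interaction to see if the association is different in the two arms". Lesion-symptom mapping is also run on change scores, and no lesion-by-arm term is named.

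Protocol 5.5.2.2 says that lesion maps from routine scans will be available for all 206 participants, "giving us sufficient power (minimum recommended N=100 [75]) for determining the lesion locations significantly associated with lower therapy response".

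**The concern.** A correlation between a baseline measure and change within one arm shows that the measure is associated with improvement. It does not show that the measure alters the effect of SIGHT, because people in either arm may improve without SIGHT. Section 5.7 itself expects natural recovery in both groups. Only a difference between arms in the association separates the two. The protocol gives power for the within-arm test and none for the difference.

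Two misreadings would follow. A within-arm correlation in the SIGHT group could be reported as a determinant of therapy response when it reflects recovery. A non-significant interaction could be read as no modification when the test had little chance of finding any. Lesion mapping on pooled change scores carries the first risk directly: a lesion site linked to poor spontaneous recovery would appear as a site linked to poor response to SIGHT.

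There is also a smaller mismatch within 5.7. The significance level is divided by two, while the same sentence applies the test to structure and function in each arm.

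**Working it through.** **Inputs from the protocol.** 40 imaged per arm with 20% attrition, so n = 40 × 0.8 = 32 analysable per arm (5.7). r = 0.58 and α = 0.025 (5.7). Lesion volume regressed out (5.10.4.1). 206 randomised with 20% dropout (5.7). The protocol does not state sidedness; two-sided is assumed.

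**Step 1: the stated figure.** Fisher z for one correlation:

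power = Φ( atanh(r)·√(n − 3) − z(1 − α/2) )

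atanh(0.58) = 0.6625 and √29 = 5.385, with product 3.567. Subtracting z = 2.241 leaves 1.326, so power is 90.8%. Simulating the t-test of r gives 91.6%. In reverse, n = ((2.241 + 1.282)/0.6625)² + 3 = 31.3, rounded up to 32, and 32/0.8 = 40 per arm. The printed calculation is therefore right for one correlation in one arm. With lesion volume partialled out, √28 replaces √29 and power is 89.7%, just under the claim.

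**Step 2: the number of tests.** Structure and function in each of two arms is 2 × 2 = 4 tests.

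- With α = 0.05/4 = 0.0125, z = 2.498 and power is Φ(3.567 − 2.498) = 85.8%. Reaching 90% would need 36 analysable, or 45 per arm with 20% attrition.
- With 2.5% kept for each test, the family-wise error over four tests is 1 − 0.975⁴ = 9.6% if they are independent, against 1 − 0.975² = 4.9% for two.

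**Step 3: the interaction.** For the difference between two independent correlations:

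power = Φ( |atanh(r₁) − atanh(r₂)| / √(2/(n − 3)) − z(1 − α/2) )

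With n = 32 per arm the standard error is √(2/29) = 0.2626. The SIGHT correlation is set at 0.58. The protocol gives no TAU correlation and no α for this test, so both are varied here as assumptions.

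| Assumed TAU r | Difference in z | Power, α = 0.05 | Power, α = 0.025 | Analysable per arm for 90%, α = 0.05 |
|---|---|---|---|---|
| 0 | 0.662 | 71% | 61% | 51 |
| 0.2 | 0.460 | 42% | 31% | 103 |
| 0.3 | 0.353 | 27% | 18% | 172 |

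Simulating a linear model with an arm-by-measure term gives slightly lower values: 67% and 56% for TAU r = 0, and 23% and 15% for TAU r = 0.3. The cited 0.58 describes neglect improvement and is not tied to SIGHT, so some correlation under TAU is plausible and the first row is the favourable case.

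**Step 4: lesion mapping.** After 20% dropout, 206 × 0.8 = 164.8, or about 165, remain over both arms. Section 5.10.4.1 maps change scores, which contain recovery in both arms and response to SIGHT in one. Without a lesion-by-arm term, a sample of this size supports mapping of recovery. It does not by itself support a statement about therapy response.

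**The case against.** The strongest reply is that 5.7 makes no error. It states a within-arm correlation, gets its power right and claims nothing for the interaction. The two correlations can be read as structure and function, adjusted within each arm, which holds the error at 5% per arm. Multiplicity for mechanistic tests is often left to the analysis plan. The interaction figures also rest on TAU correlations and an α that the protocol does not supply.

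Much of this stands. The arithmetic is correct, and the interaction power has to be shown as a range. But the protocol itself fixes an adjustment, and that adjustment does not control error over both arms or include the interaction. It also states the aim as modification and gives power for something else.

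Some stronger inferences are tempting but not supported:

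- **Eight tests.** This follows only if left and right IPS are tested separately, as objective 3 might suggest. Section 5.10.4.1 describes function as an inter-hemispheric measure, which can be read as one.
- **A large loss from the rule that "ROIs overlapping with lesion will be excluded from analysis".** The rule removes regions and does not remove patients from the trial. Section 4.1 says that the IPS is intact in most neglect cases, and no overlap rate is given from which to compute a loss.
- **Lesion mapping below the cited minimum of 100.** That arises only if mapping is confined to the SIGHT arm (103 × 0.8 = 82), an analysis the protocol does not describe. The 20% is also a 12-week rate, while the mapped outcome is at T1.
- **An inconsistent p-value for r = 0.58 with N = 25.** Whether it is inconsistent depends on the test used in a source not at hand, and no power figure changes.

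**Conclusion.** The concern holds as a mismatch between objective and power. The claim of more than 90% is sound for a single within-arm correlation of 0.58 at 2.5% (90.8%, or 89.7% with lesion volume regressed out). It says nothing about modification of the SIGHT effect. For that question, power with 32 per arm lies between about 27% and 71% at 5%, or 18% and 61% at 2.5%. These ranges assume r = 0.58 under SIGHT and 0 to 0.3 under TAU. The alpha adjustment covers two tests where the protocol's own wording gives four; the cost is power of 86%, or a family-wise error of about 10% under independence. The power statement for lesion mapping does not carry over to therapy response while the mapped outcome is change pooled over arms.

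**What to change.** - **5.7:** state that the 90% applies to one within-arm correlation of 0.58 at 2.5%. Give the interaction power as a range over stated TAU correlations and a stated α.
- **5.10.4.1:** make the arm-by-measure interaction the test of modification. Name one functional and one structural IPS summary, and let their two interaction tests share alpha. Report within-arm correlations as descriptive.
- **5.10.4.1 and 5.5.2.2:** either add a lesion-by-arm analysis, with about 165 analysable at 20% dropout, or label pooled lesion mapping as mapping of recovery. In either case remove the claim of sufficient power for therapy response.

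The cost is wording and a change in which test carries the inference. The stated power becomes less favourable. No extra scans or participants are required.

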5.8 Recruitment and Retention

5.8.1 Recruitment

For the efficacy measures, we estimate that active clinical stoke centres will recruit on average 1.2 participants per site per month to reach the required 206 participants. Acute sites that confirm they have access to a 3T MRI facility are expected to recruit 0.6 participants per site per month for the neuroimaging mechanistic measures.

Considering length of acute hospital stay, a proportion of patients are repatriated to the stroke unit in their local community hospital very soon after their stroke, sometimes within 48-72 hours. Therefore, our trial design has considered patient discharge by: 1) adding costs for 8 stroke units in community hospitals so that patients who are discharged quickly from acute to community stroke units can continue taking part; 2) reducing intervention dosage to 7 sessions over 10 days so it is feasible within the average length of hospital stay of neglect patients at our sites, 21 days; 3) not recruiting patients expecting to be discharged to their own homes in the next 7 days. The baseline mechanistic neuroimaging data will be acquired before discharge from acute centres. Remaining baseline measures can be collected in acute and community hospitals as well as outside of hospital settings (e.g., in patients' own homes).

5.8.2 Retention

To maximise retention and minimise loss to follow-up, funding has been allocated for visits at T1 and T2 to be conducted within patients' home where necessary. Also, pre-established relationships between acute and community hospitals will allow the patient data to continue to be collected and intervention sessions to conducted if they transfer between sites.

5.9 Assignment of Intervention

5.9.1 Allocation

5.9.1.1 Sequence generation -

Randomisation will be implemented by a secure web-based service provided by the NCTU after baseline measures are collected. The randomisation sequence will be stratified by clinical centre and will balance the following evidence-based factors across groups: age (18-64 or \geq 65), neglect severity (0-25 very severe or 26-51 less severe on Star Cancellation Test [17]) and preservation of the intraparietal sulcus bilaterally (yes or no) as assessed by qualified staff in the routine clinical imaging (CT and/or MRI). Age and neglect severity are included as these have been shown to significantly impact stroke recovery [59;38-39]. IPS lesion is included to balance our groups for the mechanistic analysis. Time after stroke was not included as our inclusion criteria of participants being 'less than 60-days post stroke' will ensure that all participants will complete intervention within the first 90-days post-stroke (i.e., early subacute phase [32]), which is the recommended period for all stroke recovery trials as it is a critical time for neural plasticity [31-33]. In a similar vein, participants will also be 'at

least 1-week post-stroke' thus avoiding the inclusion of the 30% of patients that show rapid neglect recovery in the first week post-stroke [86].

5.9.1.2 Allocation concealment mechanism

Web-based. Will happen after completing the baseline measures.

5.9.1.3 Allocation Implementation

The participants will be allocated to the intervention by a process embedded in the webbased data management system. The randomisation code will be saved in the study database for later decoding. When a patient is randomised, an email will be sent to the appropriate assigned research team members for the patient, to alert the research team to the start of the intervention if allocated to Arm B.

5.9.2 Blinding

The research staff delivering therapy at each site will be notified of group allocation via the NCTU secure web-based service. Group allocation will be withheld from the blinded assessors. To reduce the risk of contamination, SIGHT will be delivered in a separate treatment room and onsite monitoring of intervention delivery will review trial progress and discuss the importance of this risk. Blinded assessors will only conduct assessments at follow-up visits T1 and T2.

5.9.3 Unblinding

While every effort will be made to ensure that site staff undertaking the efficacy assessments remain unblinded, these staff will be asked to record any occurrences of unblinding.

